5.1.7. Treatment Compliance

Treatment compliance with all study-related medications should be emphasized to the subject by the site personnel, and appropriate steps should be taken to optimize compliance during the study. Compliance with INCB053914 will be calculated, by the sponsor, based on the drug accountability documented by the site staff and monitored by the sponsor/designee (tablet counts). Subjects will be instructed to bring all study-related medications with them to the study visits in order for site personnel to conduct tablet counts to assess study drug accountability. The drug accountability documentation will be used by the sponsor to calculate treatment compliance.

5.2. Treatment of Subjects

5.2.1. Starting Dose

The starting dose of INCB053914 in Part 1 will be 100 mg QD. Dose escalation in Part 1, dose-finding in Part 3, and the determination of the Part 2 monotherapy dose and Part 4 combination regimens will proceed as per Section 4.1.

5.2.2. Dose Modifications

Dose interruptions and modifications may occur for individual study subjects. The identification of DLTs will define the doses used in planned cohorts. Further, the occurrence of DLTs and other toxicities (related or unrelated to study drug) will guide decisions for treatment interruptions and discontinuation for individual subjects.

Subjects enrolled in the dose-escalation or dose-finding portion of the study will have the option of escalating to a dose found to be tolerated in a subsequent cohort (see Section 5.2.6).

5.2.3. Dose-Limiting Toxicity and Determination of Maximum-Tolerated Dose

Dose-limiting toxicity will be defined as the occurrence of any of the toxicities in Table 4 occurring up to and including Day 21 or Day 28 (per regimen cycle schedule), except those with a clear alternative explanation (eg, disease progression) or transient (≤ 72 hours) abnormal laboratory values without associated clinically significant signs or symptoms based on investigator determination. All DLTs will be assessed by the investigator using CTCAE v4.03 criteria. Subjects who receive at least 80% of the INCB053914 doses at the level assigned 80% of the planned doses for the SOC agents or have a DLT will be considered evaluable for determining tolerability of the dose. Subjects receiving dose reductions (but not meeting DLT criteria) that result in $< 80\%$ of the prescribed dose being administered will not be considered evaluable for the purposes of determining the MTD and will be replaced.

Individual subject dose reductions may be made based on events observed at any time during treatment with study drug; however, for the purposes of dose cohort escalation/de-escalation/dose-finding and determining the MTD of INCB053914 monotherapy or the optimal doses of INCB053914 in combination with the selected SOC agents, decisions will be made based on events that are observed from the first day of study drug administration through and including the final day of Cycle 1 (Day 21 or Day 28). A lower MTD may subsequently be determined based on relevant toxicities that become evident after Day 21 or Day 28, respectively.

CONFIDENTIAL

CONFIDENTIAL

Table 4: Definition of Dose-Limiting Toxicity

Toxicity		
Nonhematologic		

 Any \geq Grade 3 nonhematologic toxicity EXCEPT the following: 
 Nausea, vomiting, and diarrhea responding to supportive therapy within 48 hours. Alopecia 		
Hematologic^a		
Parameter	Treatment Group	Toxicity
Anemia	Part 1 TGB	Grade 4, unexplained by underlying disease.
	Part 1 TGA Part 3 C-TGA, C-TGB, C-TGC	Not applicable.
Neutropenia	Part 1 TGB	Grade 4 lasting > 5 days.
	Part 1 TGA Part 3 C-TGA, C-TGB	Grade 4 with a hypocellular bone marrow lasting \geq 6 weeks after the start of a course in the absence of residual disease.
	Part 3 C-TGC	Grade 4 lasting > 3 days after ruxolitinib interruption (to rule out ruxolitinib related transient decreases in WBCs because of margination). (When the clinical status of the subject allows, investigators are encouraged to wait 24 hours before starting myeloid growth factors to determine if WBC margination is contributing to the degree of neutropenia.)
Febrile neutropenia	Part 1 TGB	Febrile neutropenia of any duration (ANC < $1.0 \times 10^9/L$ and fever $\geq 38.5^\circ C$).
	Part 1 TGA Part 3 C-TGA, C-TGB	Not applicable.
	Part 3 C-TGC	Grade 4 febrile neutropenia that does not clinically resolve within 7 days in the setting of optimal interventions.
Thrombocytopenia	Part 1 TGB	Grade 4 or Grade 3 with bleeding, or any requirement for platelet transfusion.
	Part 1 TGA Part 3 C-TGA, C-TGB	Grade 4 with a hypocellular bone marrow lasting \geq 6 weeks after the start of a course in the absence of residual disease.
	Part 3 C-TGC	Grade 4 thrombocytopenia with bleeding.
TGB only: A treatment delay > 14 days because of a hematologic toxicity of any grade will also be considered a DLT.		
Other toxicities not meeting DLT criteria:		

 While the rules for adjudicating DLTs in the context of dose escalation are specified above, an AE not listed above may be defined as a DLT after a consultation with the sponsor and investigators, based on the emerging safety profile. 		

ANC = absolute neutrophil count.

^a Cytopenias and/or myelosuppression are expected outcomes of the disease processes of and treatments used for the malignancies evaluated in Part 1 TGA and Part 3 C-TGA, C-TGB, and C-TGC and per se will not constitute DLTs except as noted in this table.

CONFIDENTIAL

CONFIDENTIAL

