4.1.1. Part 1 Monotherapy Dose Escalation

Between 3 and up to approximately 30 subjects will be enrolled into each of 2 treatment groups. Treatment Group A will include acute leukemia, high-risk MDS, and MDS/MPNs (including aCML, CMML, MDS/MPN-U, and RARS-T). Treatment Group B will include MM, lymphoma, and other lymphoproliferative neoplasms. Dose escalation for TGA and TGB will proceed independently, with each treatment group following a 3 + 3 design. At least 3 subjects will be enrolled and treated in each cohort. If no DLTs are observed in the initial 3 subjects, the next cohort will begin enrollment at the next higher dose level. If 1 DLT is observed in the first 3 subjects, 3 additional subjects will be enrolled in that cohort. If a DLT occurs in one-third or more of the total cohort (ie, ≥ 2 of 6 subjects), then the MTD will be deemed to have been exceeded, and the next lower dose level will be deemed to be the MTD. Thus, the MTD will be defined as 1 dose level below that at which one-third or more of subjects in a particular cohort report DLTs. If the first cohort exceeds the MTD, a dose de-escalation will be considered. The

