4.1.3.1. Standard-of-Care Agent Combination Cohort Dose-Finding Strategy

Between 3 and up to approximately 10 subjects will be enrolled into cohorts under each of the SOC treatment groups, C-TGA, C-TGB, and C-TGC, as described above. Dose-finding for C-TGA, C-TGB, and C-TGC will proceed independently, with each treatment group following a 3 + 3 cohort design. At least 3 subjects will be enrolled and treated at each dose level. If no DLTs are observed in the initial 3 subjects, the next cohort will begin enrollment at the next higher dose level of INCB053914. If 1 DLT is observed in the first 3 subjects, 3 additional subjects will be enrolled in that cohort. If a DLT occurs in one-third or more of the total cohort (ie, ≥ 2 of 6 subjects), then the MTD will be deemed to have been exceeded, and the next lower dose level will be deemed to be the MTD. Thus, the MTD will be defined as 1 INCB053914 dose level below that at which one-third or more of subjects in a particular cohort report DLTs. If the first cohort exceeds the MTD, a dose de-escalation of INCB053914 will be considered.

A conventional regimen of the SOC agents will be used in all dose-finding cohorts within a given SOC combination treatment group and will remain fixed throughout the dose-finding portion of the study.

The starting dose of INCB053914 in the combination treatment groups will be a PAD and 1 dose level below the highest tolerated dose of INCB053914 monotherapy identified in Part 1 of this study. At the current data cutoff date, the highest tolerated dose of INCB053914 monotherapy was 80 mg BID, which also met the criteria of protocol-defined PAD; thus, the planned starting dose for Part 3 will be 65 mg BID (Dose Level 1 dose). The INCB053914 dose used in Part 3

CONFIDENTIAL

CONFIDENTIAL

will never exceed the monotherapy MTD dose to be identified in Part 1 of the study. [Table 1](#), [Table 2](#), and [Table 3](#) summarize the planned starting doses to be used in the SOC combination dose-finding cohorts. An alternative starting dose and/or subsequent INCB053914 doses (Dose Level 1, 2, and/or 3) may be selected pending emerging safety, PK, and PD data in Part 1.

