4.3.2. Replacement of Subjects

In Part 1 and Part 3, if a subject is not evaluable (eg, at least 80% of the prescribed study drug and SOC agent doses during the first cycle are not taken due to dose interruption, reduction, or discontinuation), another subject will be enrolled at this dose level. Subjects who report DLTs will be considered evaluable for the purpose of determining the safety and tolerability of the dose.

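### The two hematologic DLTs listed for TGA, C-TGA and C-TGB take 6 weeks to be met, but the 3+3 decision is made on data to Day 21 or 28

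*Protocol*

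**What the plan says.** Protocol Section 5.2.3 defines a DLT as a Table 4 toxicity occurring up to and including Day 21 or Day 28, by regimen. For escalation, de-escalation and the MTD, only Cycle 1 is used: "decisions will be made based on events that are observed from the first day of study drug administration through and including the final day". The next sentence allows, but does not require, a lower MTD to be set later from toxicities that emerge after that day.

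For Part 1 TGA and Part 3 C-TGA and C-TGB, Table 4 lists neutropenia and thrombocytopenia only if Grade 4, with hypocellular marrow, lasting at least "6 weeks after the start of a course in the absence of residual disease". For the same groups it marks anemia and febrile neutropenia as not applicable. The remaining hematologic trigger is restricted: "TGB only: A treatment delay > 14 days because of a hematologic toxicity of any grade will also be considered a DLT". Footnote a says that in these groups, and in C-TGC, cytopenias "per se will not constitute DLTs except as noted in this table". A separate row of Table 4 lets an unlisted AE be made a DLT after consultation between sponsor and investigators.

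The escalation rule in Section 4.1.1 reads "If no DLTs are observed in the initial 3 subjects, the next cohort will begin enrollment at the next higher dose level"; Section 4.1.3.1 repeats it for the combinations. Under Section 5.2.3, subjects without a DLT whose dose reductions bring them below 80% of the prescribed dose "will not be considered evaluable for the purposes of determining the MTD and will be replaced". Section 4.3.2 extends replacement to interruption and discontinuation, and treats subjects with DLTs as evaluable.

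**The concern.** Two toxicities that the sponsor chose to list as dose-limiting cannot act at the decision they are meant to inform. Followed as written, the 3+3 count in these three groups contains no listed hematologic DLT at all.

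This matters most in Part 3. Section 1.4.1 attributes marrow hypocellularity in animals to PIM inhibition, and Section 1.4.3.1 describes cytarabine as strongly marrow-suppressive. Section 1.4.4 expects no overlap between the agents, but says that they have not been combined clinically and that the safety of the combinations is unknown. Failure of the marrow to recover after leukemia has cleared is the event that Table 4 was written to catch. The dose chosen in Part 3 passes to Part 4, and the optional L-DAC cohort may lean on C-TGA tolerability (Section 4.1.4).

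The decision not to count ordinary cytopenia, anemia or febrile neutropenia in these diseases is deliberate and is not questioned here.

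**Working it through.** The plan states no figure to reproduce on this point. The check is one of timing.

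1. **Inputs.** Cycle length is 21 days in Part 1 TGA and Part 3 C-TGA and 28 days in Part 3 C-TGB (SAP Section 4.1.5). Persistence needed is 6 weeks from the start of a course (Table 4).
2. **Gap.** 6 × 7 = 42 days. TGA and C-TGA: 42 − 21 = 21 days after the window closes. C-TGB: 42 − 28 = 14 days after. Neither criterion can be satisfied inside the window in any of the three groups.
3. **Other listed hematologic triggers in these groups.** Anemia: none. Febrile neutropenia: none. Treatment delay over 14 days: TGB only. Section 5.2.4 likewise evaluates Cycle 1 hematologic dose holds as potential DLTs only for Part 1 TGB.
4. **Dose steps exposed in Part 3 (Tables 1 and 2).** 80/65 = 1.23 and 100/80 = 1.25, so +23% and +25%. Section 4.1.3.1 caps the dose at the monotherapy MTD.
5. **Loss through the 80% rule, at BID dosing.** A 21-day cycle has 42 doses; 80% is 33.6, so 9 missed doses (4.5 days) make a subject without a DLT non-evaluable. A 28-day cycle has 56 doses; 80% is 44.8, so 12 missed (6 days) do so. How often a cytopenia leads there depends on Table 5. In Part 3 its platelet and neutrophil triggers apply only to subjects with baseline platelets below 75 or ANC below 1.0 (× 10⁹/L). Even then it advises considering a hold only if neither the disease nor the standard agent explains the fall. In TGA a hold follows suspected causality. The path exists but is narrow.
6. **Direction of the effect, on assumed rates.** The documents give no aplasia rate, so these inputs are assumptions. The chance of escalating past a dose is P = (1−p)³ + 3p(1−p)⁵, where p is the counted DLT probability. Take a nonhematologic DLT rate of 10% and independent prolonged aplasia at 10%, 20% or 30%.
   - Aplasia not counted: p = 0.10, P = 0.906 in every case.
   - Aplasia counted: p = 1 − 0.9 × 0.9 = 0.19, P = 0.730; p = 1 − 0.8 × 0.9 = 0.28, P = 0.536; p = 1 − 0.7 × 0.9 = 0.37, P = 0.360.

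Step 6 assumes that the count alone drives escalation. It shows direction only and is not an estimate for this trial.

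**The case against.** The strongest reply is that this is a coherent design: escalate on an early window and let later toxicity correct the MTD. Section 5.2.3 provides for that correction in so many words. Review before further dosing is also required. Section 5.2.3.3 schedules conferences to agree on escalation, Section 8.7 requires meetings to reach consensus on tolerability, and SAP Section 11 has the sponsor decide from current safety data whether, and at what dose, to treat more subjects. Grade 3 or higher infection or bleeding in Cycle 1 can still count as a nonhematologic DLT. The DLTs reported in Section 1.4.2 are rash and ALT elevation.

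Much of this stands, and it rules out several stronger readings that a reader might infer:

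- That late aplasia can never affect dose. It can, through a later lower MTD or the required reviews.
- That footnote a shuts the consultation route. It exempts cytopenias except as noted in the table, and the consultation row is in that table.
- That escalation is automatic after 0 of 3. Reviews come first, although their outcome is a judgment.
- That the 80% rule routinely removes these subjects. Table 5 makes that path narrow.

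One might also read the DLT definition as requiring only onset by Day 21 or 28, with persistence confirmed later. The decision sentence refers to events observed in Cycle 1, so the cohort would still be decided before confirmation.

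What survives is that none of these routes requires a confirmed 6-week event to be counted, or escalation to wait for one. SAP Section 11 itself has the sponsor apply the existing escalation rules.

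**Conclusion.** The inconsistency is real and sits within one section: two listed DLTs need about 42 days, and the rule that uses them stops at Day 21 or 28. At the decision they contribute nothing to the 3+3 count in TGA, C-TGA or C-TGB, and afterwards they act only at discretion. This should be fixed.

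The practical weight is in Part 3. In TGA, 115 mg BID had already been declared nontolerated and a 100 mg BID cohort opened (Section 1.4.2). The consequence is limited to two planned steps of 23% and 25% under the monotherapy cap. The documents do not support a claim that an unsafe dose was or will be selected: they give no rate of prolonged aplasia and do not show which cohorts remain undecided. The conclusion rests on the text and on scheduled cycle lengths, not on the illustrative probabilities.

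**What to change.** Amend Section 5.2.3 for Part 1 TGA and Part 3 C-TGA and C-TGB, for cohorts still to be decided:

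1. For the two 6-week criteria in Table 4, run the window to Day 42 from the start of Cycle 1. All other DLTs keep Day 21 or 28.
2. A confirmed event counts as a DLT at the dose at which it arose, even if the subject was replaced. The 3+3 rule for that dose level must then be re-applied. For these two criteria this replaces the optional later lowering of the MTD.
3. At the Cycle 1 cohort review, flag as pending any subject with unresolved Grade 4 neutropenia or thrombocytopenia that was not Grade 4 at baseline and whose available marrow shows no residual leukemia. Escalation waits for recovery, documented residual disease or Day 42. The baseline condition is needed because Section 3.3 sets no hematologic entry criteria for these groups.
4. Subjects with no marrow result are not automatically pending; they are adjudicated at the existing review. Marrow comes only from examinations already provided for or clinically indicated (for example Table 9 footnote i, Table 12 footnote j, Section 7.6.3). In C-TGA the first may fall as late as Day 15 + 14 = Day 29.

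The cost is amendment wording plus a delay of up to 3 weeks (TGA, C-TGA) or 2 weeks (C-TGB) in cohorts with a pending subject, which may not be rare with cytarabine. No new visit or test is needed. C-TGA already has counts on Days 22, 32 (± 4) and 43 (Table 10), and unrecovered C-TGB subjects are seen weekly after Day 28 (Table 12 footnote c).

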5.1.6. Ruxolitinib

In the Part 3 C-TGC dose-finding cohorts and Part 4 C-TGC E1 expansion cohort, ruxolitinib ([Jakafi 2016](#)) will be administered as an open-label commercial BID oral treatment using the dose designated as the stable dose at the time of the screening visit for each subject. Acceptable doses are 5 mg BID to 25 mg BID.

Doses of ruxolitinib should be self-administered approximately 12 hours apart without regard to food.

Note that subjects must be instructed to withhold the morning dose of ruxolitinib until reaching the clinic for each study visit where administration will occur. The dose may need to be reduced or interrupted for declining platelet count or ANC as described in Section 5.2.4 and will be increased or restarted with recovery of hematologic parameters.

Ruxolitinib should be stored in accordance with the Jakafi[®] package insert.

CONFIDENTIAL

CONFIDENTIAL

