5.2.4. Criteria and Procedures for Dose Interruptions and Adjustments of Study Drug

Treatment with INCB053914, L-DAC, azacitidine, or ruxolitinib may be delayed up to 2 weeks (≤ 14 days) to allow for resolution of toxicity. The second induction or consolidation cycles of I-DAC may be delayed until subject has recovered from I-DAC-related toxicities. Subjects may resume treatment if no medical condition or other circumstance exists that, in the opinion of the investigator, would make the subject unsuitable for further participation in the study. The treating investigator should contact the sponsor to discuss the case of any subject whose treatment has been delayed for more than 14 days before restarting treatment with INCB053914, L-DAC, azacitidine, or ruxolitinib.

Because subjects may enter the study with extensive pretreatment and/or severe bone marrow infiltration by the primary disease, these dose reduction rules are provided as guidelines (see [Table 5](#)). Individual decisions regarding dose reduction should be made using clinical judgment and in consultation with the sponsor's medical monitor, taking into account relatedness of the AE to the study drug or SOC agents, and the subject's underlying condition. Adverse events that have a clear alternative explanation or transient (≤ 72 hours) abnormal laboratory values without associated clinically significant signs or symptoms may be exempt from dose-reduction rules. Hematologic events (eg, thrombocytopenia, anemia, neutropenia) occurring in Part 1 TGB precipitating dose interruptions during Cycle 1 of treatment will be evaluated as potential DLTs ([Table 4](#)) and managed as per the guidelines in Section 5.2.3. Hematologic AEs that precipitate dose interruptions should be monitored for recovery at least every 3 days, if feasible.

CONFIDENTIAL

CONFIDENTIAL

Table 5: Guidelines for Interruption and Restarting of Study Drug

CHEMISTRY		
Adverse Event	Trigger	Action Taken
ALT and/or AST elevation	Grade 1	
 Continue study drug: 
 –Monitor LFTs at least weekly until < Grade 1 or baseline. –Carefully examine subject's concomitant medications for any that may contribute to LFT elevations. Hold these concomitant medications or switch to an alternative; consult medical monitor if needed. –Subjects with persistent but stable low-grade elevations (eg, < 1.5 × ULN) may revert to the routine LFT evaluation schedule as noted in Section 6.

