ANC ($\times 10^9/L$)	Part 1 TGB Part 2 TGB Expansion Cohorts	< 0.5	
 Hold until resolved to ≥ 0.5. If recovery to ≥ 0.5 in ≤ 7 days, restart study drug at same dose and monitor. If recovery to ≥ 0.5 in > 7 days, restart study drug at next lower dose and monitor.
	Part 1 TGA Part 2 TGA Expansion Cohorts	N/A	Neutropenia should be managed as per institutional standard, relevant to the underlying disease. If there is a suspected causal relationship to INCB053914 in the setting of a decreasing ANC, hold INCB053914 and discuss with the medical monitor.
	Part 3 All Cohorts Part 4 All Cohorts	$\geq 50\%$ decrease from baseline ANC (Subjects with baseline ANC < 1.0 only)	
 Evaluate underlying disease based on peripheral blood and bone marrow assessment as needed. Consider dose interruption if cytopenias are NOT due to underlying disease or treatment with standard-of-care agents. Restart study drug at next lower dose (or 25% reduction if in expansion cohort, rounded down to the nearest tablet strength); monitor as clinically indicated.

CONFIDENTIAL

CONFIDENTIAL

Table 5: Guidelines for Interruption and Restarting of Study Drug (Continued)

HEMATOLOGY			
Parameter	Subjects	Trigger	Action Taken
Hemoglobin (g/dL)	All treatment groups/cohorts	< 6.5	
 Hold until resolved to ≥ 6.5, restart at same dose, and monitor. If recovery to ≥ 6.5 does not occur within 14 days of dose interruption or is refractory to transfusion support, discontinue study drug treatment(s) and follow-up per Protocol.
OTHER TOXICITIES			
Adverse Event		Action Taken	
Any Grade 1 or Grade 2 toxicity.		Continue study drug treatment and treat the toxicity; monitor as clinically indicated.	
Any Grade 3 toxicity, if clinically significant and not manageable by supportive care.		
 Interrupt study drug up to 2 weeks (14 days), until toxicity resolves to \leq Grade 1 or to baseline. Resume study drug at same dose. If assessed as related to study drug, resume at next lower dose (or 25% reduction, whichever is the smaller increment, rounded down to the nearest pill strength); monitor as clinically indicated. 	
Any recurrent Grade 3 toxicity after 2 dose reductions.		Discontinue study drug and follow-up per Protocol. (Exceptions require approval of sponsor.)	
Any other Grade 4 toxicity.		Discontinue study drug and follow-up per Protocol.	

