Note: Dose reductions in Part 2 or Part 4 will use the next lowest dose evaluated in Part 1 or combination regimen in Part 3, respectively.

Up to 2 dose reductions of cytarabine, azacitidine, and ruxolitinib may be made at the discretion of the investigator.

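### In Part 3 C-TGC the only afebrile neutropenia DLT presupposes a ruxolitinib hold that the protocol never requires, so prolonged Grade 4 neutropenia can miss the written criterion

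*Protocol*

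**What the plan says.** **The criterion.** Protocol Section 5.2.3, Table 4, gives C-TGC one afebrile neutropenia DLT: "Grade 4 lasting > 3 days after ruxolitinib interruption". The row explains that the hold is there to exclude a transient, margination-related fall in white cells. The only other neutropenia entry for C-TGC is febrile: Grade 4 and unresolved within 7 days. The DLT for a treatment delay beyond 14 days applies to TGB only. Footnote a says that cytopenias in C-TGC are not DLTs in themselves unless the table says so. The table also lets the sponsor and investigators declare an unlisted event a DLT after consultation.

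**Ruxolitinib management.** Section 5.1.6 says: "The dose may need to be reduced or interrupted for declining platelet count or ANC as described in Section 5.2.4". Section 5.2.4 says that treatment with "azacitidine, or ruxolitinib may be delayed up to 2 weeks". The notes to Table 5 add: "Up to 2 dose reductions of cytarabine, azacitidine, and ruxolitinib may be made at the discretion of the investigator". The Table 5 ANC row for Parts 3 and 4 is limited to "Subjects with baseline ANC < 1.0 only". It suggests considering an interruption if the cytopenia is not attributed to the disease or to the standard-of-care agent, and then says "Restart study drug at next lower dose (or 25% reduction if in expansion cohort, rounded down to the nearest tablet strength".

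**Evaluability.** Under Sections 4.3.2 and 5.2.3, a subject without a DLT who receives less than 80% of planned doses is not evaluable and is replaced. A subject with a DLT is always evaluable. Section 4.1.3.1 declares the MTD exceeded at 2 or more DLTs in 6.

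**The concern.** The more-than-3-day clock starts at a ruxolitinib interruption. If that interruption is optional, so is the clock. Two subjects with the same prolonged afebrile Grade 4 neutropenia can then be classified differently: a DLT if ruxolitinib was held, and no written DLT if it was continued or only reduced. The second subject may leave the denominator through replacement, or stay in it as having tolerated the dose.

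DLTs are part of the primary safety endpoint and drive the C-TGC 3 + 3 decision. The event is also foreseeable. Section 1.3.3 describes neutropenia on ruxolitinib as dose-related and reports it in 15.3% of subjects at any grade. Section 1.4.1 reports lower neutrophil counts in dogs at all INCB053914 doses in the 28-day study. Section 1.4.4 says that the safety of the combinations is unknown.

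**Working it through.** The plan gives no DLT rate or operating characteristic for C-TGC, so there is no figure to reproduce. The check is a reading of the text, a dose count, and an illustration under assumed rates.

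**1. Is the hold required anywhere?** Section 5.1.6 says that the dose may need to be reduced or interrupted, and a reduction is not an interruption. It refers to Section 5.2.4, which permits a delay of up to 14 days, leaves ruxolitinib reductions to the investigator, and has no ANC threshold for ruxolitinib. The Table 5 ANC row speaks of restarting study drug. Section 5.2.4 names study drug separately from the combination agents ("taking into account relatedness of the AE to the study drug or SOC agents"), so the row reads as concerning INCB053914. The SAP adds no DLT definition that would close the gap. The hold is nowhere required.

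**2. What happens to prolonged afebrile Grade 4 neutropenia?**

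| Ruxolitinib | INCB053914 doses received | Written result |
|---|---|---|
| Held, Grade 4 persists > 3 days | any | DLT, evaluable |
| Continued or only reduced | < 80% | No written DLT, replaced |
| Continued or only reduced | 80% or more | No written DLT, evaluable |

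**3. When does INCB053914 fall below 80%?** Dosing is BID. SAP Section 4.1.5 gives C-TGC a 21-day cycle, and Protocol Section 5.2.3 allows Day 21 or Day 28, so both are shown.

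- 21 days: 42 doses, and 0.80 × 42 = 33.6, so 34 are needed. 34/42 = 0.810 passes and 33/42 = 0.786 fails, so 9 missed doses are enough. A 4-day hold leaves 34/42; a 5-day hold leaves 32/42 = 0.762.
- 28 days: 56 doses, and 0.80 × 56 = 44.8, so 45 are needed. 45/56 = 0.804 passes and 44/56 = 0.786 fails, so 12 missed doses are enough. A 5-day hold leaves 46/56 = 0.821; a 6-day hold leaves 44/56.

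**4. Effect on the 3 + 3 rule (illustration).** Let r be the true rate of events that would meet the criterion if ruxolitinib were held, and s the share that are counted. Both are assumptions. No other type of DLT is included. With q the effective DLT rate, a dose clears with probability

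Pass(q) = (1 − q)³ + 3q(1 − q)² × (1 − q)³.

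- All events counted: q = r.
- Uncounted subjects stay evaluable: q = r·s.
- Uncounted subjects are replaced: q = r·s / [1 − r(1 − s)].

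Example with r = 0.20 and s = 0.5. All counted: 0.8³ + 3(0.2)(0.8²)(0.8³) = 0.512 + 0.197 = 0.709. Stay evaluable: q = 0.10, Pass = 0.906. Replaced: q = 0.10/0.90 = 0.111, Pass = 0.887.

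Columns for s show replaced / stay evaluable.

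| r | All counted | s = 0.9 | s = 0.75 | s = 0.5 |
|---|---|---|---|---|
| 0.05 | 0.973 | 0.978 / 0.978 | 0.984 / 0.985 | 0.993 / 0.993 |
| 0.10 | 0.906 | 0.921 / 0.922 | 0.941 / 0.944 | 0.971 / 0.973 |
| 0.20 | 0.709 | 0.744 / 0.752 | 0.798 / 0.814 | 0.887 / 0.906 |

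**The case against.** The best reply is that the intent is plain and that several checks would catch a missed case. Ruling out margination requires a hold, Section 5.1.6 anticipates interruption for falling ANC, and Section 6.2.2 plans C-TGC visits while ruxolitinib is on hold. Dose-reduction decisions are made in consultation with the medical monitor (Section 5.2.4). The cohort calls exist partly to adjudicate high-grade events as possible DLTs (Section 5.2.3.3), and subject-level teleconferences run weekly or every two weeks (Section 8.7). The consultation clause sits inside Table 4, so footnote a does not block it. A lower MTD can be set later (Section 5.2.3), and INCB053914 never exceeds the monotherapy MTD (Section 4.1.3.1).

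All of this stands, and it lowers the chance that an event is lost and limits the harm. It does not supply the missing rule: each route for declaring a DLT is a matter of judgement.

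The same reading rules out some stronger inferences:

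- A reader might infer that Table 5 steers investigators away from holding ruxolitinib. It does not. It suggests an interruption only where the cytopenia is not attributed to the disease or the combination agent, and the row covers only subjects with a low baseline ANC.
- A reader might apply the row "Any other Grade 4 toxicity", which stops study drug, to neutropenia. That is strained: ANC has its own hematology block, and the row is not cohort-specific. It would also stop INCB053914 permanently in AML subjects on cytarabine for a cytopenia that footnote a calls expected.
- A reader might take the note in exclusion criterion 3, that C-TGC subjects stay on ruxolitinib, as barring a hold. It qualifies a washout criterion and is not a toxicity rule.

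**Conclusion.** The point holds as a gap in the written DLT rule. Whether prolonged afebrile Grade 4 neutropenia counts in C-TGC depends on a ruxolitinib hold that the criterion presupposes and the protocol leaves optional. Where ruxolitinib is not held, the subject may be replaced or may count as having tolerated the dose. Only discretionary review corrects this.

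The size is unknown. The documents give neither a rate of this event for the combination nor the share of cases in which ruxolitinib would be held; the 15.3% figure is any-grade neutropenia on ruxolitinib alone. Under the assumed inputs, the effect is small if the event is rare or ruxolitinib is usually held, and material only if the event is common and often uncounted. The documents do not support an inference that such events would routinely be lost, or that C-TGC escalation is unsafe as planned. This is a cheap improvement of minor to moderate severity.

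**What to change.** State in Section 5.2.4, and repeat in the Table 4 C-TGC neutropenia row, that ruxolitinib is interrupted when Grade 4 ANC is documented within the DLT window. The clock then always starts, the margination rationale is kept, and the cross-reference in Section 5.1.6 has a rule to point to.

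The cost is a wording amendment with no added visits. The clinical downside is a short ruxolitinib hold in some subjects who would otherwise have continued or reduced it.

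No rule is needed to keep every held subject evaluable. Neutropenia persisting beyond 3 days after the hold is a DLT, and that subject is already evaluable. A 4-day hold of a BID drug still leaves 34/42 = 81% of doses. A subject without a DLT who falls below 80% should stay under the existing replacement rule; counting that subject as evaluable would treat an under-dosed subject as having tolerated the dose.
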